4.1.2. Baseline data

The flow of patients, including the overall eligible patients, excluded patients and patients in the analytic dataset will be presented in a Figure (Figure 1). We will present demographic and clinical characteristics for all patients and by age (<12 and >=12 years) and MISC status (Table 1). Continuous variables will be summarized as means with standard deviations or medians with observed range or interquartile range and compared between groups with independent t-test or Mann-Whitney U test as appropriate. Categorical variables will be summarized as counts with percentages and compared using the Chi-squared test or Fishers exact test as appropriate. All statistical analyses will be performed with SAS v 9.4

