# H. Data Analysis Plan:

The statistical analysis plan was developed by the lead trial biostatistician. Subject demographics and characteristics at study entry will be summarized with counts and percentages for categorical variables, and with means, standard deviations, medians, and interquartile ranges (IQR) as appropriate, for numeric variables. Missing data will not be imputed. Analysis of the primary endpoint will be conducted on the safety population, which includes all subjects who receive at least one dose of enoxaparin. The primary endpoint, cumulative incidence of ISTH-defined [11] clinically-relevant bleeding events during hospitalization, will be calculated with the corresponding exact (Clopper-Pearson) 90% confidence intervals (90%CIs). The precision of estimates for different cumulative incidences of clinically-relevant bleeds and corresponding 90% Cis are as follows: 0/38, 0% (0-7.6)%; 1/38, 2.6% (0-11.8%); 2/38, 5.3% (0-15.7%). The secondary endpoint, twice-daily enoxaparin dose required to achieve target anti-Xa levels, will be summarized

with medians and IQRs for all the study participants combined and by age group. Medians will be compared across age groups, if there are adequate numbers in the groups, using the Kruskal-Wallis test and a *post-hoc* Bonferroni-adjusted Mann-Whitney U test, if needed. The tertiary endpoints (as outlined in Section IV.B) will be calculated as proportions and cumulative incidences with 90%CIs, and medians with IQRs.

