2. STUDY DESIGN

The study is a phase 2, single-arm, open-label, non-randomized clinical trial conducted at 12 centers in the US to evaluate the safety, dose-requirements, and exploratory efficacy of twice-daily subcutaneous enoxaparin as in-hospital venous thromboembolism (VTE) prophylaxis in children (birth to 18 years) hospitalized with signs and/or symptoms of SARS-CoV-2 infection (i.e., COVID-19) including COVID-19 multisystem inflammatory syndrome (MISC)

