2.5. SAMPLE SIZE

The study enrolled 38 participants

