4. STATISTICAL METHODOLOGY

4.1. GENERAL METHODOLOGY

Data analysis for this study will be performed at the JHAC DCC-PMCS at study completion, once the database has been locked and the Statistical Analysis Plan has been finalized and approved by the study team.

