4.3. ANALYSIS OF THE SECONDARY OUTCOME

The secondary endpoint, twice-daily enoxaparin dose required to achieve target anti-Xa levels, will be summarized with medians and IQRs for all the study participants combined and by age group and MISC status. Distributions will be compared across groups, if there are adequate numbers in the groups, using Mann-Whitney U test.

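### SAP 4.1.2 and 4.3 add comparisons at age 12 and by MIS-C status that the protocol does not plan, and do not mark them as additions

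*SAP*

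**What the plan says.** **Protocol.** Section IV.H treats baseline data as description only: "Subject demographics and characteristics at study entry will be summarized with counts and percentages for categorical variables", with means, medians and spread for numeric variables. The only between-group test it names is for dose requirement across age groups, by Kruskal-Wallis with Bonferroni-adjusted Mann-Whitney follow-up, if the groups are large enough. Specific Aim 2 (section I.B) defines four age bands: birth to <1, 1 to <6, 6 to <13 and 13 to <18 years. The multisystem inflammatory syndrome (CMIS in the protocol, MIS-C in the SAP) appears as a second route of entry in IV.E.2, not as a comparison group.

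**SAP.** Section 2 describes the design: "The study is a phase 2, single-arm, open-label, non-randomized clinical trial". Section 2.5 reads "The study enrolled 38 participants". Section 4.1.2 presents characteristics for all patients, at ages <12 and >=12, and by MIS-C status. Continuous items are "compared between groups with independent t-test or Mann-Whitney U test as appropriate" and categorical items "compared using the Chi-squared test or Fishers exact test as appropriate". Section 4.3 summarises dose "by age group and MISC status" and compares groups by Mann-Whitney U, with no adjustment. Section 4.4 gives the tertiary outcomes by the same groupings and names no test. No significance level is stated, and no section describes the MIS-C or age-12 groupings as additions to the protocol.

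**The concern.** A reader of the final report needs to know which comparisons the protocol set out and which came later. Here the SAP presents the added groupings beside the planned dose analysis, without a label and without a reason for cutting at 12. A small p-value for MIS-C status or for age 12 could then be given the same standing as the protocol's age-band test of Hypothesis 2. With 38 children and no adjustment, that would be more weight than such a result can bear.

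Separately, several of the baseline tests answer no real question, because the variable tested helps to define the groups or necessarily follows from them.

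**Working it through.** The plan gives no number of tests and no error level, so there is no planned figure to reproduce. The check is mainly a comparison of texts.

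**1. What is new in the SAP**

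| Item | Protocol | SAP |
|---|---|---|
| Baseline characteristics | Summaries only (IV.H) | Tests by age <12/>=12 and by MIS-C status (4.1.2) |
| Dose by age | Four bands (I.B); Kruskal-Wallis, Bonferroni follow-up (IV.H) | Age group not defined in 4.3; Mann-Whitney U, no adjustment |
| Dose by MIS-C status | None | Mann-Whitney U (4.3) |
| Tertiary outcomes by group | None | Estimates by age group and MIS-C status, no test (4.4) |

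**2. The cut at 12.** The protocol's boundaries are 1, 6 and 13 years. Twelve lies inside the 6 to <13 band, so no merging of planned bands gives <12 versus >=12. SAP 1.2 still lists the four bands. Mann-Whitney U compares two groups, which fits a split at 12 better than four bands, but SAP 4.3 does not say which is meant.

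**3. Timing.** SAP 2.5 reports enrolment in the past tense, and SAP 4.5 does the same for precision. That indicates wording after enrolment. The SAP text available carries no date, so this is an inference from tense. SAP 4.1 places the analysis "once the database has been locked and the Statistical Analysis Plan has been finalized and approved by the study team"; it does not require the SAP to be final before enrolment ends.

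**4. Tests that carry little information**
- Age is listed in SAP 3.3.1 and would be tested between groups defined by age.
- Weight must follow age over the range from birth to <18 years.
- Coagulopathy by PT, PTT or D-dimer is one of five qualifying features for MIS-C, of which two or more are needed (Protocol IV.E.2; SAP 2.3). Testing those variables by MIS-C status is therefore partly circular, to the extent that MIS-C status follows the entry definition.

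**5. Scale, as an illustration only**
- Items in SAP 3.3.1: age, gender, weight, BMI (4); white cells, haemoglobin, platelets (3); PT, PTT, INR, fibrinogen, D-dimer, creatinine (6). Total 4 + 3 + 6 = 13.
- Two splits, less age tested by age: 13 × 2 − 1 = 25 tests.
- Expected false positives at an assumed alpha of 0.05, if no true difference existed: 25 × 0.05 = 1.25.

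The expected count does not need the tests to be independent. It does need both the assumed alpha and the absence of any true difference, and step 4 shows that the latter is unrealistic for several items.

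**The case against.** The defence has real substance.

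- **The comparisons are written down before analysis.** SAP 4.1 puts analysis after database lock and SAP approval, and the methods sections are in the future tense. Calling the groupings post hoc is therefore contestable. This stands, and the accurate description is that they are not in the protocol and appear in text worded after enrolment.
- **MIS-C is a natural division.** The protocol itself has two sets of entry criteria, so describing the cohort by MIS-C status is reasonable. This stands for description; it does not make a test of dose by MIS-C status a planned one.
- **Tests in a baseline table are common and drive no decision.** True, which keeps the point minor. It does not make the age-by-age test informative.
- **The tertiary outcomes are already exploratory.** SAP 1.3 and 3.3 say so, and 4.4 names no test. There are no p-values to remove there; only the groupings lack a label.

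A reader might infer that an unblinded team picked the groups after looking at the data. The documents do not support that: an open-label design and a past-tense sentence show neither when the groups were chosen nor that anyone had looked at results by group. A reader might also turn the test count into a high probability of at least one false positive. That would need independent tests, yet PT and INR are closely related, as are weight and BMI. It would also need a null hypothesis true for every item. Adding the measures in SAP 3.3.2 to the count is not justified either, since length of stay, mortality and discharge medication are not baseline data.

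**Conclusion.** The point holds as a matter of labelling and of restraint in testing. SAP 4.1.2 and 4.3 add comparisons that the protocol does not contain, the cut at 12 cannot be built from the planned bands, and nothing tells the reader so. Some of the baseline tests are uninformative whatever their timing.

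The consequence is small. The primary bleeding estimate and its 90% confidence interval are unaffected; what is at risk is the interpretation of secondary and descriptive comparisons. The figure of about 1.25 false positives in 25 tests should be quoted, if at all, only with its assumptions. The conclusion rests on the texts as they stand and on reading the past tense of SAP 2.5 as wording after enrolment. If a dated SAP version showed that the groupings were set earlier, the words *added after enrolment* would go, but the departure from the protocol would remain.

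**What to change.** 1. **SAP 4.1.2:** remove the between-group tests, so that Table 1 is descriptive as in Protocol IV.H. The age and MIS-C columns may stay.
2. **SAP 4.3:** keep the protocol's Kruskal-Wallis test across the four age bands, with Bonferroni-adjusted follow-up and the condition of adequate numbers, as the planned test of Hypothesis 2. Removing p-values for age altogether would lose the only test of that hypothesis, so the removal should cover the added splits only.
3. **SAP 4.3 and 4.4:** label any <12/>=12 or MIS-C breakdown *not in the protocol, added after enrolment, exploratory*, and report it as estimates with intervals.

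If the analysis has already been run, the same label belongs in the report.

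The cost is a few lines of SAP wording and fewer outputs. The downside is that no p-values stand beside the added descriptive columns. Sample size and the primary analysis do not change.

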4.1.3. Distributional assumptions

- The distribution of continuous variables will be evaluated for normality.

4.1.4. Handling of missing data

The analysis for all the Aims will be a complete case analysis. Missing data will not be imputed.

4.1.5. Protocol violations and patient withdrawals

All deviations / violations to the protocol (if applicable) will be summarized using counts and frequencies. Similarly, reasons for early withdrawal from the study will be summarized using counts and frequencies.

4.2. ANALYSIS OF THE PRIMARY OUTCOME

The primary endpoint, cumulative incidence of ISTH-defined clinically-relevant bleeding events during hospitalization, will be calculated with the corresponding exact (Clopper-Pearson) 90% confidence intervals (90%Cls)

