The Schedule of Assessments is shown in Table 1. SAE monitoring and safety laboratory monitoring occurs on days 1-3, and on days 7 and 14 if the patient is still hospitalized. For all participants, pertinent clinical data will be captured as follows: results of coagulation and thrombophilia testing; nature of any major or clinically-relevant non-major bleeding episodes (as defined in Section IV B, above) during the anticoagulant therapy period (with detail as to amount of any related blood transfusion and/or any other intervention required—see also Data and Safety Monitoring Plan section); and nature of any new onset VTE (with detail as to signs/symptoms and anatomic site). PDFs of the REDCap electronic case report forms (eCRFs), as well as SAE report forms, are provided in the Manual of Operations. All SAEs and enoxaparin regimen adherence will be tracked

throughout hospitalization, and SAEs will continue to be tracked through 30 days postenrollment.

Children will complete their participation in the trial at the 30 days (+/- 2 days) postenrollment end-of-study telephone visit. As noted previously, the primary safety endpoint collection also occurs at the 30 days (+/- 2 days).

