# E. Description of Population to be Enrolled

#### 1. Target Enrollment

The target accrual is based on the primary endpoint (safety). The safety population is defined as all patients who received at least one dose of the enoxaparin regimen. In order to achieve adequate power and precision for determination of safety in the primary analysis (see also section G, below), the target enrollment is 38 evaluable children, from among a total of 12-15 participating sites. Participants who do not received at least one dose of the enoxaparin regimen (i.e. early termination, withdrawal of consent) will be replaced. Anticipating an 85% retention rate, we will enroll up to 45 participants. Both males and females of all races and ethnic groups are eligible for this study.

Table 1. Schedule of Assessments.

Assessment	Screening (Within 72 hours of hospital admission)	Enrollm ent Day 0	Day 1	Day 2	Day 3 *	Day 7 *	Day 14 *	Day 30 (+/- 2 days)
Informed consent		Х						
Enrollment		Х						
Full H&P	Х							
Focused H&P			Х	Х	Х	Х	Х	
Weight	Х							
CBC with platelet count	Х				Х	Х	Х	
PT and aPTT 	Х				Х	Х	Х	
Fibrinogen 	Х				Х	Х	Х	
Serum creatinine	Х				Х	Х	Х	
Urine pregnancy screen 	Х							
Research blood specimen 		Х	Х	Х	Х	Х	Х	
Anti-factor Xa level 			Х	+/- X				
SAE Monitoring			Х	Х	Х	Х	Х	Х
Bleeding event (based on focused interim H&P)			Х	Х	Х	Х	Х	Х
VTE event (based on focused interim H&P, with radiological confirmation when suspected clinically)			х	х	х	х	х	х
Telephone visit 								Х

Obtained for research purposes if not already being obtained clinically.

 For participants <20kg: (1) 3ml blue top tube and (1) 4mL CPT Tube (7mL total). For participants  $\ge$ 20kg, (1) 3mL blue top tube and (2) 4mL CPT tubes (11mL total). Research blood collection is for central research lab testing of D-dimer, Clot Formation and Lysis (CloFAL) assay, IL-6, and anti-SARS-CoV-2 IgG, as well as banking plasma, DNA isolated from the buffy coat, and peripheral blood mononuclear cells (PBMCs) for future research.

 Obtained at 4 hours after 1st or 2nd dose of enoxaparin, at initial dosage (mg/kg) and any subsequent change in dosage.

Focused, scripted assessment of symptoms of potential concern for bleeding events, VTE events, and SAEs. Refer to Manual of Operations.

\* If still hospitalized.

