#### Day 2 after enrollment (as inpatient)

- Interval focused interim history and physical with assessment for serious adverse events, bleeding event, and/or VTE event by inpatient medical provider
- Anti-factor Xa level (if enoxaparin dose sub- or supratherapeutic)
- Research blood specimen

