#### Day 3 after enrollment (if still hospitalized)

- Interval focused interim history and physical with assessment for serious adverse events, bleeding event, and/or VTE event by inpatient medical provider
- Repeat plasma laboratory evaluation including the following (obtained as research purposes if not already obtained clinically)
  - Complete blood cell count with platelet count
  - PT and aPTT
  - Fibrinogen
  - Serum creatinine
- Research blood specimen

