#### 30 days (+/- 2 days) after enrollment

Patient will be assessed for SAEs, bleeding events, and VTE events via telephone call with a study team member using a standardized screening script.

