3. OUTCOME VARIABLES

3.1. PRIMARY OUTCOME(S)

Safety: Occurrence of clinically-relevant (i.e., major plus clinically relevant non-major [CRNM]) bleeding within 30 days.

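### The primary bleeding outcome is defined over 30 days but calculated over the hospital stay, and neither document says which window is primary

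*SAP*

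**What the plan says.** The definition is the same in both documents. SAP 3.1 gives the primary outcome as "Occurrence of clinically-relevant (i.e., major plus clinically relevant non-major [CRNM]) bleeding within 30 days", and Protocol IV.A uses the same words.

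The calculation is also the same in both documents, but over a different window. Protocol IV.H sets the primary endpoint as the "cumulative incidence of ISTH-defined [11] clinically-relevant bleeding events during hospitalization", and SAP 4.2 as the "cumulative incidence of ISTH-defined clinically-relevant bleeding events during hospitalization". Both attach an exact Clopper-Pearson 90% interval.

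Collection is described as follows.

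- Protocol IV.D states that "the primary safety endpoint collection also occurs at the 30 days (+/- 2 days" and times that visit from enrollment. The same section also describes capturing bleeding episodes over the period of anticoagulant therapy.
- Protocol Table 1 has a row "Bleeding event (based on focused interim H&P" that is marked through to the day-30 column. For the day-30 visit, Protocol IV.F says "Patient will be assessed for SAEs, bleeding events, and VTE events via telephone call".
- Protocol IV.J.3 collects SAEs from enrollment to the end of the 30-day window and treats major and clinically relevant non-major bleeds as SAEs of particular interest.
- The visit list moves from "Day 2 after enrollment (as inpatient" to "Day 3 after enrollment (if still hospitalized", and days 7 and 14 carry the same condition as day 3.

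Specific Aim 1 gives no window in either document.

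**The concern.** This is the trial's only primary estimate, and two sections of the same SAP describe different quantities. An analyst who follows SAP 4.2 to the letter leaves out a bleed that SAP 3.1 counts and that the day-30 call is there to find. An analyst who follows SAP 3.1 includes it.

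Hypothesis 1 is set at the one-bleed case: an observed incidence of at most 2.6%, with an upper 90% limit of at most 11.8%. At that margin a single child decides whether the result is consistent with the hypothesis, so the conclusion can turn on which sentence is followed. The trial is open-label, and a window chosen once the bleeds are known would be hard to defend.

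**Working it through.** **Inputs.** n = 38 (Protocol IV.E.1; SAP 2.5 and 4.5). Two-sided exact 90% interval (Protocol IV.H, SAP 4.2). Hypothesis 1 limits of 2.6% and 11.8% (Protocol I.B).

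**Formula.** For x bleeds among n children, the lower limit is the 0.05 quantile of Beta(x, n − x + 1), or 0 when x = 0. The upper limit is the 0.95 quantile of Beta(x + 1, n − x).

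**Reproducing the plan's figures.** For x = 0 the upper limit is 1 − 0.05^(1/38) = 7.58%.

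| x/n | Estimate | Exact 90% CI, recomputed | Printed in Protocol IV.H and SAP 4.5 |
|---|---|---|---|
| 0/38 | 0% | 0 to 7.58% | 0 to 7.6% |
| 1/38 | 2.63% | 0.135 to 11.885% | 0 to 11.8% |
| 2/38 | 5.26% | 0.943 to 15.656% | 0 to 15.7% |
| 3/38 | 7.89% | 2.186 to 19.159% | not given |

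The printed upper limits reproduce to within 0.1 point; 11.885% appears to have been truncated to 11.8%. The printed lower limits of 0 for one and two bleeds are not the exact ones. That is a separate and minor matter, but it is why the intervals quoted here differ slightly from the printed ones.

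**Where the windows part.** Classify each child by the first clinically-relevant bleed after enrollment.

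| First bleed | SAP 3.1, 30 days | SAP 4.2, hospital stay |
|---|---|---|
| In hospital, by day 30 | counted | counted |
| After discharge, by day 30 | counted | not counted |
| In hospital, after day 30 | not counted | counted |
| After discharge, after day 30 | not counted | not counted |

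The second row is the one for which the schedule is built. A child discharged on day 2 has 30 − 2 = 28 further days inside the 30-day definition that SAP 4.2 does not count. The third row needs a stay beyond day 30. Protocol IV.D ends participation at the day-30 visit, so no later collection is planned for such a bleed.

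**Size.** Each child in the second row adds 1/38 = 2.63 points to the 30-day estimate and nothing to the in-hospital one. With n held at 38:

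| In-hospital bleeds by day 30 | Post-discharge first bleeds by day 30 | SAP 4.2 | SAP 3.1 |
|---|---|---|---|
| 0 | 1 | 0% (0-7.6%) | 2.6% (0.1-11.9%) |
| 1 | 1 | 2.6% (0.1-11.9%) | 5.3% (0.9-15.7%) |
| 2 | 1 | 5.3% (0.9-15.7%) | 7.9% (2.2-19.2%) |
| 0 | 2 | 0% (0-7.6%) | 5.3% (0.9-15.7%) |

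The second line is the critical one. SAP 4.2 returns the 1/38 case on which Hypothesis 1 is built. SAP 3.1 returns 5.3% against 2.6% and an upper limit of 15.7% against 11.8%, so both limits are exceeded.

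**The case against.** The strongest defence is that bleeding during the hospital stay is a sensible quantity for this drug. Protocol IV.D gives the regimen to inpatients only, Aim 1 concerns in-hospital thromboprophylaxis, and Protocol IV.K.3 expects no raised bleeding risk beyond 12 hours after the regimen stops. An incidence over the exposure period does not need the same length for every child. Protocol IV.D also mentions bleeding capture over the anticoagulant therapy period, so the collection text does not speak with one voice. The analysis is descriptive, both estimates can be computed from the same data, and they may turn out identical.

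All of this stands, and it justifies reporting the in-hospital figure. It does not settle which figure is primary. The outcome as defined counts every clinically-relevant bleed in the window, whether or not the drug caused it. Protocol IV.K.3 itself provides for bleeds that develop after discharge. That SAP 3.3.2 lists discharge on thromboprophylaxis as a variable favours neither window clearly.

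A reader might draw three stronger conclusions that the documents do not support.

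- *That SAP 4.2 will understate bleeding.* It might, but no post-discharge rate is given, and a first in-hospital bleed after day 30 would push the other way.
- *That outcome data are lost.* They are not: bleeding is collected to day 30 whichever window is analysed.
- *That SAP 4.1.1, which refers to outcome determination within 30 days of COVID diagnosis, removes children whose call was on schedule.* That follows only if diagnosis means the qualifying test and determination means the day-30 call, and neither term is defined. If the inpatient assessments count as determination, most of the supposed exclusion disappears.

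**Conclusion.** The contradiction is real, stands in current text, and occurs within each document: definition in Protocol IV.A and SAP 3.1, calculation in Protocol IV.H and SAP 4.2. Because it concerns the sole primary endpoint, it should be settled before the primary analysis.

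The 30-day window is the better supported, given the stated time of endpoint collection, the day-30 bleeding assessment and the 30-day SAE window. The reference to the therapy period keeps that support short of unanimous.

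The consequence is 2.63 points per child with a first bleed between discharge and day 30, and at one in-hospital bleed it is enough to carry the result past both Hypothesis 1 limits. These figures assume that all 38 children are evaluable under either window. How likely such a bleed is cannot be stated from the documents; with no bleed in either disputed period, the two estimates are equal.

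**What to change.** 1. In Protocol IV.H and SAP 4.2, replace the reference to hospitalization with *within 30 days of enrollment*, which matches the defined outcome and the origin from which it is collected.
2. Report in-hospital bleeding, with the same exact 90% interval, as one supportive row labelled as such.
3. Report how many children have no day-30 telephone contact. The 30-day count relies on that call, the SAP uses complete cases without imputation (4.1.4), and loss to follow-up is foreseen (Protocol IV.F), so the 30-day denominator could fall below 38.

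The cost is one phrase in each document, one table row and one count. No new data are needed: Protocol IV.I records dates of events, and SAP 3.3.2 lists length of stay.

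If SAP 4.1.1 is revised at the same time, align it with the protocol's safety population in IV.E.1 and IV.H, which is every child who received at least one dose. Do not write in a requirement for outcome determination at day 30. Read literally, that would remove a child who bleeds in hospital and then dies or is lost before day 28: 1/38 would become 0/37, an estimate of 0% with upper limit 1 − 0.05^(1/37) = 7.8%.
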